4 SUBJECT SELECTION CRITERIA

For entry into the study, the following criteria **MUST** be met. No exceptions from the protocol-specific selection criteria will be approved.

4.1 Inclusion Criteria

- 1) Willing and able to give written informed consent.
- 2) Histologic diagnosis of melanoma.
- 3) First episode of radiological evidence of brain metastases
- 4) Age > 18 years.
- 5) RTOG-RPA class 2 (Table 1)
- 6) Karnofsky performance status (PS) > 70%. (Appendix 1)
- 7) Barthel Index of Activities of Daily Living > 10 (Appendix 2)
- 8) Measurable disease (mWHO criteria).
- 9) Adequate organ function as determined by the following criteria:
 - a. WBC \geq 2000/uL
 - b. Absolute neutrophil count (ANC) $> 1.5 \times 10^9/L$.
 - c. Platelet count $> 75 \times 10^9/L$.
 - d. Hemoglobin > 9 g/dL. If the patient received a RBC transfusion, the required value of hemoglobin should be met at least 1 week after the most recent transfusion.
 - e. Serum creatinine $\leq 2.0 \times$ ULN.
 - f. Serum aspartate aminotransferase (AST) and serum alanine aminotransferase (ALT) $\leq 2.5 \times$ ULN for patients without liver metastasis, or ≤ 5 times for liver metastases.
 - g. Total bilirubin $\leq 2.0 \times$ ULN, (except patients with Gilbert's Syndrome, who must have a total bilirubin less than 3.0 mg/dL)
 - h. Albumin > 2.5 g/dL
- 10) Persons of reproductive potential must agree to use an adequate method of contraception throughout treatment and for at least 26 weeks after ipilimumab is stopped:
 - a. WOCBP include any female who has experienced menarche and who has not undergone successful surgical sterilization (hysterectomy, bilateral tubal ligation, or bilateral oophorectomy) or is not post-menopausal. WOCBP must have a negative serum or urine pregnancy test (minimum sensitivity 25 IU/L or equivalent units of HCG) within 72 hours before the start of ipilimumab. If the pregnancy test is positive, the patient must not receive ipilimumab and must not be enrolled in the study. Before study enrollment, women of childbearing potential (WOCBP) must be advised of the importance of avoiding pregnancy during study participation and the potential risk factors for an unintentional pregnancy. WOCBP must be using an adequate method of contraception to avoid pregnancy throughout the study and for up to 26 weeks after the last dose of investigational product, in such a manner that the risk of pregnancy is minimized. In general, the decision for appropriate

methods to prevent pregnancy should be determined by discussions between the investigator and the study subject.

- Post-menopause is defined as:
 - i. Amenorrhea \geq 12 consecutive months without another cause, or
 - ii. For women with irregular menstrual periods and taking hormone replacement therapy (HRT), a documented serum follicle stimulating hormone (FSH) level \geq 35 mIU/mL.
- Women who are using oral contraceptives, other hormonal contraceptives (vaginal products, skin patches, or implanted or injectable products), or mechanical products such as an intrauterine device or barrier methods (diaphragm, condoms, spermicides) to prevent pregnancy, or are practicing abstinence or where their partner is sterile (eg, vasectomy) should be considered to be of childbearing potential.
- b. Men of fathering potential must be using an adequate method of contraception to avoid conception throughout the study, and for up to 26 weeks after the last dose of investigational product in such a manner that the risk of pregnancy is minimized.

4.2 Exclusion Criteria

- 1) Patients with melanoma and brain metastases with any of the following disease-specific characteristics:
 - a. Documented evidence of prior progression of melanoma to an ipilimumab-containing regimen (i.e. received at least 2 doses of ipilimumab for either advanced disease or in the adjuvant setting and the disease progressed/relapsed -according to mWHO criteria- within 24 weeks since the first dose of ipilimumab)
 - b. Prior radiation therapy to the brain
 - c. Other prior antineoplastic therapies for brain metastases.
 - d. Patients with cerebral metastases as the only location of the disease, for which local therapy (neurosurgery, radiosurgery) could achieve a disease-free status
 - e. Patients with a rapid clinical deterioration, or with risk of herniation, or who require unstable ascending dosing of supportive medication in the last week -including anti-convulsants, steroids and analgesics-, or who require dexamethasone > 16 mg/d (or other glucocorticoid at an equipotent dose), or with a high LDH ($> 2 \times$ ULN).
- 2) Any other malignancy form which the patient has been disease-free for less than 5 years, with the exception of adequately treated and cured basal or squamous cell skin cancer, superficial bladder cancer or carcinoma in situ of the cervix, or incidental prostate cancer.
- 3) Uncontrolled diabetes mellitus (HbA1c $> 9\%$)
- 4) Autoimmune disease other than vitiligo or past thyroiditis under substitutive hormone therapy: Patients with a history of inflammatory bowel disease, including ulcerative colitis and Crohn's Disease, are excluded from this study, as are patients with a history of symptomatic disease (eg, rheumatoid arthritis, systemic progressive sclerosis [scleroderma], systemic lupus erythematosus, autoimmune vasculitis [eg, Wegener's Granulomatosis]); motor neuropathy considered of autoimmune origin (e.g. Guillain-Barre Syndrome and Myasthenia Gravis).

- 5) Other chronic intestinal diseases associated with diarrhea.
- 6) Active infection or other serious illness or medical condition.
- 7) Known active or chronic infection with HIV, Hepatitis B, or Hepatitis C.
- 8) Therapy with any of the following: IL-2, interferon, or other non-study immunotherapy regimens; cytotoxic chemotherapy; immunosuppressive agents; target molecular inhibitors (BRAF, MEK, KIT); or chronic use of systemic corticosteroids (used for the management of non-cancer related illnesses), either concomitantly or during the last 3 weeks prior to the beginning of the treatment.
- 9) Any experimental therapy administered in the past 30 days prior to the beginning of the treatment.
- 10) Any non-oncology vaccine therapy used for the prevention of infectious diseases (for up to 4 weeks prior to or after any dose of blinded study drug)
- 11) Women of childbearing potential (WOCBP), as defined above in “Inclusion criteria”, who:
 - a. are unwilling or unable to use an acceptable method of contraception to avoid pregnancy for their entire study period and for at least 26 weeks after cessation of study drug, or
 - b. have a positive pregnancy test at baseline, or
 - c. are pregnant or breastfeeding.
- 12) Prisoners or subjects who are compulsorily detained (involuntarily incarcerated) for treatment of either a psychiatric or physical (eg, infectious) illness.
- 13) Any other general, medical or psychological conditions which in the opinion of the investigator will make the administration of ipilimumab hazardous, or that would preclude appropriate informed consent or compliance with the protocol, or obscure the interpretation of eventual AEs.

4.3 **Data Safety Monitoring Plan**

A Data Safety Monitoring Committee (DSMC) will be designated prior to the initiation of the study, and chaired by the coordinating principal investigator. The DSMC will meet approximately every 4 months to ensure that subject safety is carefully monitored. The DSMC might also be consulted on an *ad-hoc* basis should a safety signal emerge, and may also convene an *ad-hoc* meeting on its own initiative. Following the review, the DSMC will recommend continuation, modification, or discontinuation of the study based on observed toxicities.

The DSMC will have access to reports of study data including analyses addressing population characteristics, dosing, safety, and efficacy updated as available prior to each of its meetings.

5. **STUDY THERAPY**

5.1. **Ipilimumab**

5.1.1. **Dose Calculations**

Each patient will receive ipilimumab 3 mg/Kg every 3 weeks, for a total of 4 administration. Infusions should be given over 90 minutes (not bolus or IV push).

Calculate **Total Dose** as follows:

$$\text{Patient body weight in kg} \times (x) \text{ mg} = \text{total dose in mg}$$

Calculate **Total Infusion Volume** as follows:

$$\text{Total dose in mg} \div 5 \text{ mg/mL} = \text{infusion volume in mL}$$

Calculate **Rate of Infusion** as follows:

$$\text{Infusion volume in mL} \div 90 \text{ minutes} = \text{rate of infusion in mL/min.}$$

For example, a patient weighing 75 kg would be administered 225 mg of ipilimumab ($75 \text{ kg} \times 3 \text{ mg/kg} = 225 \text{ mg}$) with an infusion volume of 45 mL ($225 \text{ mg} \div 5 \text{ mg/mL} = 45 \text{ mL}$) at a rate of approximately 0.5 mL/min ($45 \text{ mL} \div 90 \text{ minutes}$) in 90 minutes.

The total dose must be calculated using the most recent subject weight (obtained within 3 days of the dosing visit, and prior to the infusion).

The maximum dose of ipilimumab per cycle is 400 mg. Therefore, patients $\geq 133 \text{ kg}$ should not receive a dose $> 400 \text{ mg}$ per cycle.

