5.1.2. Storage, Preparation, and Administration

Ipilimumab injection must not be administered as an IV push or bolus injection. Care must be taken to assure sterility of the prepared solutions, since the drug product does not contain any antimicrobial preservatives or bacteriostatic agents.

- Do not shake product.
- Inspect parenteral drug products visually for particulate matter and discoloration prior to administration. Discard vial if solution is cloudy, there is pronounced discoloration (solution may have pale yellow color), or there is foreign particulate matter other than translucent-to-white, amorphous particles.

Preparation of Solution

- Allow the vials to stand at room temperature for approximately 5 minutes prior to preparation of infusion.
- Withdraw the required volume of ipilimumab and transfer into an intravenous bag.
- Dilute with 0.9% Sodium Chloride Injection, USP or 5% Dextrose Injection, USP to prepare a diluted solution with a final concentration ranging from 1 mg/mL to 2 mg/mL. Mix diluted solution by gentle inversion.
- Store the diluted solution for no more than 24 hours under refrigeration (2°C to 8°C , 36°F to 46°F) or at room temperature (20°C to 25°C , 68°F to 77°F).
- Discard partially used vials or empty vials of ipilimumab.

Administration Instructions

- Do not mix ipilimumab with, or administer as an infusion with, other medicinal products.

- Flush the intravenous line with 0.9% Sodium Chloride Injection, USP or 0.5% Dextrose Injection, USP after each dose.
- Administer diluted solution over 90 minutes through an intravenous line containing a sterile, non-pyrogenic, low-protein-binding in-line filter.

See the current Summary of product characteristics (SMPC) Brochure for additional information on allowable filter types. The infusion must be completed in 90 minutes with an 10 ml normal saline flush at the end.

Ipilimumab should be administered under the supervision of a physician experienced in the use of intravenous (IV) agents. Ipilimumab is administered as an IV infusion only.

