7.1. Identification

Ipilimumab is available in concentrations of 5 mg/mL (50 mg/10 mL and 200 mg/40 mL). The sterile solution in the vial is clear and colorless. Ipilimumab is administered via intravenous infusion only.

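### Section 5.1.1 computes the infusion volume and pump rate from the undiluted vial concentration, so both are 2.5 to 5 times too low for the diluted bag that section 5.1.2 requires

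*Protocol*

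**What the plan says.** Section 5.1.1 (Dose Calculations) sets the dose: "Each patient will receive ipilimumab 3 mg/Kg every 3 weeks, for a total of 4 administration". It then gives three formulas: dose in mg from body weight; total infusion volume as dose divided by 5 mg/mL; and rate as that volume divided by 90 minutes. The worked example is a 75 kg patient who receives 225 mg "with an infusion volume of 45 mL" "at a rate of approximately 0.5 mL/min". The section contains no dilution step. It caps the dose at 400 mg per cycle.

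Section 7.1 (Identification) shows where the 5 mg/mL comes from: "Ipilimumab is available in concentrations of 5 mg/mL". It is the strength of the product in the vial.

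Section 5.1.2 (Storage, Preparation, and Administration) describes a different solution going into the patient. The pharmacy is told to "Withdraw the required volume of ipilimumab and transfer into an intravenous bag", and then to add saline or dextrose "to prepare a diluted solution with a final concentration ranging from 1 mg/mL to 2 mg/mL". The administration instruction is "Administer diluted solution over 90 minutes through an intravenous line", and the section adds "The infusion must be completed in 90 minutes".

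**The concern.** The two sections describe different bags. Section 5.1.1 calculates as though undiluted 5 mg/mL drug were infused; section 5.1.2 requires a solution of 1–2 mg/mL. A rate of 0.5 mL/min for 90 minutes empties a 45 mL bag, but under section 5.1.2 no bag for a 225 mg dose is that small.

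What is at stake is correct administration of the study drug. The rate in section 5.1.1 is the only one in mL/min that the protocol calculates, and other instructions build on it. Section 5.1.8 refers back to the planned initial rate when an infusion is completed or resumed after a reaction, including restarting at half of it. Section 5.1.9 halves the previous rate for recurrent drug fever. A wrong starting rate would carry into those steps. The example applies at 12 sites, up to four times per patient.

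**Working it through.** **Inputs.** Dose 3 mg/kg, example weight 75 kg, infusion time 90 minutes and cap 400 mg (section 5.1.1); vial strength 5 mg/mL (section 7.1); final concentration 1–2 mg/mL and completion in 90 minutes (section 5.1.2).

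**The plan's own figures.**
- Dose = 75 × 3 = 225 mg
- Volume = 225 / 5 = 45 mL
- Rate = 45 / 90 = 0.5 mL/min

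These reproduce exactly, so the division is sound. The question is which volume it describes.

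**The same patient with the solution section 5.1.2 requires.** Bag volume = dose / final concentration; rate = bag volume / 90; diluent = bag volume − 45 mL.

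| | As printed (5 mg/mL) | 2 mg/mL | 1 mg/mL |
|---|---|---|---|
| Volume infused | 45 mL | 225 / 2 = 112.5 mL | 225 / 1 = 225 mL |
| Diluent added | none | 112.5 − 45 = 67.5 mL | 225 − 45 = 180 mL |
| Rate over 90 min | 0.5 mL/min | 112.5 / 90 = 1.25 mL/min | 225 / 90 = 2.5 mL/min |
| Ratio to printed | 1 | 2.5 | 5 |

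**Other weights.** For dose D and final concentration c, the ratio is (D / c) / (D / 5) = 5 / c, so D cancels. It is 2.5 at 2 mg/mL and 5 at 1 mg/mL for every patient. At the 400 mg cap, the section 5.1.1 formula gives 400 / 5 = 80 mL and 80 / 90 = 0.89 mL/min. Section 5.1.2 requires 400 / 2 = 200 mL to 400 / 1 = 400 mL, at 200 / 90 = 2.22 to 400 / 90 = 4.44 mL/min.

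**If the 75 kg diluted bag were run at the printed rate.**
- Time to empty: 112.5 / 0.5 = 225 minutes, or 225 / 0.5 = 450 minutes.
- If stopped at 90 minutes, 0.5 × 90 = 45 mL has been given: 45 × 2 = 90 mg (90 / 225 = 40% of the dose) or 45 × 1 = 45 mg (45 / 225 = 20%).

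The last line needs two conditions together: the printed rate is used on the diluted bag, and the infusion is ended at 90 minutes with most of the bag unused.

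**The case against.** The strongest reply is that the protocol still leads a careful site to the right result. Every division in section 5.1.1 is correct, and 45 mL is the right amount of drug to draw up; section 5.1.2 asks for a required volume without giving a formula, and section 5.1.1 supplies it. Duration is the controlling parameter. It is 90 minutes throughout, and section 5.1.2 makes completion in that time mandatory. Since a range of concentrations is allowed, the pump has to be set from the prepared bag anyway. The delivered-dose shortfall requires a site to discard 60–80% of a prepared dose, and a slow infusion would be noticed, because section 6.4.1.b has vital signs taken every 30 minutes. The error runs in the slow direction and cannot cause an overdose. Section 6.3.1 also lists Drug Preparation Guidelines, which may already be right.

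Much of this stands. The fault is a mislabelled quantity carried into a rate, and the under-dosing case is conditional. Two things do not go away. Reading 45 mL as the volume to withdraw rescues that number but not the rate, which section 5.1.1 derives from it explicitly. And no text reconciles the sections: no undiluted option is offered, and the 10 mL flush cannot account for the gap. The preparation guidelines are not among the documents; if they give the correct rate, they contradict the protocol, which section 10.1 says must be followed.

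**Conclusion.** The concern holds. Section 5.1.1 states an infusion volume and rate that are too low by a factor of 2.5 (at 2 mg/mL) to 5 (at 1 mg/mL) for the solution section 5.1.2 requires, whatever the patient's weight. For the 75 kg example the correct figures are 112.5–225 mL at 1.25–2.5 mL/min. The result rests only on the protocol's own concentrations and its 90-minute duration.

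The consequence is bounded. The mg dose is right, and the sample size and statistical analysis are untouched. Following the 90-minute rule with the actual bag delivers the full dose. Following the printed rate with that bag is a protocol deviation, and an under-dose only if the infusion is also stopped at 90 minutes. How likely sites are to do either cannot be judged from these documents. It must still be corrected, because a written instruction for giving the investigational drug is wrong and conflicts with the section that follows it.

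**What to change.** In section 5.1.1:

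- Relabel dose / 5 mg/mL as the volume of concentrate to withdraw.
- Add the dilution step, with total infusion volume defined as the diluted bag volume: dose / final concentration, at 1–2 mg/mL.
- Define the rate as the diluted bag volume / 90 minutes.
- Replace the 75 kg example with: 225 mg; withdraw 45 mL; add 67.5–180 mL of diluent to make 112.5–225 mL; infuse at 1.25–2.5 mL/min over 90 minutes.

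If the sponsor does intend to permit undiluted infusion, section 5.1.2 must say so and give it its own rate.

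The cost is a few lines of protocol text, plus a check that the Drug Preparation Guidelines listed in section 6.3.1 state the same volumes and rate. The dose, data collection and analysis do not change.

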5.1.2. Storage, Preparation, and Administration

Ipilimumab injection must not be administered as an IV push or bolus injection. Care must be taken to assure sterility of the prepared solutions, since the drug product does not contain any antimicrobial preservatives or bacteriostatic agents.

- Do not shake product.
- Inspect parenteral drug products visually for particulate matter and discoloration prior to administration. Discard vial if solution is cloudy, there is pronounced discoloration (solution may have pale yellow color), or there is foreign particulate matter other than translucent-to-white, amorphous particles.

Preparation of Solution

- Allow the vials to stand at room temperature for approximately 5 minutes prior to preparation of infusion.
- Withdraw the required volume of ipilimumab and transfer into an intravenous bag.
- Dilute with 0.9% Sodium Chloride Injection, USP or 5% Dextrose Injection, USP to prepare a diluted solution with a final concentration ranging from 1 mg/mL to 2 mg/mL. Mix diluted solution by gentle inversion.
- Store the diluted solution for no more than 24 hours under refrigeration (2°C to 8°C , 36°F to 46°F) or at room temperature (20°C to 25°C , 68°F to 77°F).
- Discard partially used vials or empty vials of ipilimumab.

Administration Instructions

- Do not mix ipilimumab with, or administer as an infusion with, other medicinal products.

- Flush the intravenous line with 0.9% Sodium Chloride Injection, USP or 0.5% Dextrose Injection, USP after each dose.
- Administer diluted solution over 90 minutes through an intravenous line containing a sterile, non-pyrogenic, low-protein-binding in-line filter.

See the current Summary of product characteristics (SMPC) Brochure for additional information on allowable filter types. The infusion must be completed in 90 minutes with an 10 ml normal saline flush at the end.

Ipilimumab should be administered under the supervision of a physician experienced in the use of intravenous (IV) agents. Ipilimumab is administered as an IV infusion only.

5.1.3. Dose Modification

Ipilimumab Dose Skipping Rule

Decisions to skip an ipilimumab dose must be made on specified safety criteria. Treatment with ipilimumab will be skipped or discontinued if the subject experiences at least one adverse event, specified below, considered by the investigator to be **“possibly,” “probably,” or “certainly” related to ipilimumab treatment.** The investigator should contact the Sponsor for any adverse event that will prompt a skipped dose or discontinuation of ipilimumab.

The following criteria will be used to determine dose skipping, restarting doses, or discontinuing ipilimumab.

It may be necessary to skip study drug dosing for the following related adverse event(s):

- Any \geq Grade 2 non-skin related adverse event (including immune-mediated adverse reactions), except for laboratory abnormalities
- Any \geq Grade 3 laboratory abnormality
- Any adverse event, laboratory abnormality or intercurrent illness that, in the judgment of the investigator, presents a substantial clinical risk to the subject with continued dosing.

It is necessary to skip study drug dosing for the following adverse events:

- Any \geq Grade 3 skin related adverse event regardless of causality.

Restart ipilimumab dosing if/when the adverse event(s) resolve(s) to \leq Grade 1 severity or returns to baseline within 2 weeks of initial dose administration:

- If the adverse event has resolved, restart ipilimumab dosing at the next scheduled timepoint per protocol.
- If the adverse event has not resolved in the protocol-specified dosing window (3 weeks [\pm 3 days]), the next scheduled dose will be skipped and dosing will be resumed at the subsequently scheduled dose.
- If $>$ 1 dose is expected to be skipped, the dosing schedule modifications must be discussed with the principal investigator prior to implementation.

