5.1.5. Permanent Discontinuation of Ipilimumab

5.1.5.a Permanent Discontinuation for Related Adverse Events

Permanently discontinue ipilimumab for any of the following:

- Persistent moderate adverse reactions or inability to reduce corticosteroid dose to 7.5 mg prednisone or equivalent per day (due to an AE).
- Failure to complete full treatment course within 18 weeks from administration of first dose.
- Severe or life-threatening adverse reactions, including any of the following:
 - Colitis with abdominal pain, fever, ileus, or peritoneal signs; increase in stool frequency (7 or more over baseline), stool incontinence, need for intravenous hydration for more than 24 hours, gastrointestinal hemorrhage, and gastrointestinal perforation
 - Aspartate aminotransferase (AST) or alanine aminotransferase (ALT) >5 times the upper limit of normal or total bilirubin >3 times the upper limit of normal
 - Stevens-Johnson syndrome, toxic epidermal necrolysis, or rash complicated by full thickness dermal ulceration, or necrotic, bullous, or hemorrhagic manifestations
 - Severe motor or sensory neuropathy, Guillain-Barré syndrome, or myasthenia gravis
 - Severe immune-mediated reactions involving any organ system (eg, nephritis, pneumonitis, pancreatitis, non-infectious myocarditis)
 - Immune-mediated ocular disease that is unresponsive to topical immunosuppressive therapy

- Any adverse event, laboratory abnormality or intercurrent illness which, in the judgment of the investigator, presents a substantial clinical risk to the patient with continued dosing.
- The development of progression (irPD) in the global tumor burden confirmed by serial imaging 4-6 weeks later and/or clinical deterioration of subject's condition such that further benefit from ipilimumab dosing is unlikely or requires a change of therapy.

Please refer to the IB for specific treatment algorithms.

The following neurological adverse event requires permanent discontinuation of ipilimumab and defines unacceptable neurotoxicity:

- Any motor neurologic toxicity \geq Grade 3 regardless of causality
- Any \geq Grade 3 treatment related sensory neurologic toxicity

Please refer to the IB for specific treatment algorithms.

5.1.5.b Exceptions to Permanent Discontinuation

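### One investigator-judged risk trigger means skip-and-restart in 5.1.3 but a permanent stop in 5.1.5.a; 5.1.3 lacks a liver carve-out, and 5.1.4 withdraws patients whom Section 3 keeps in follow-up

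*Protocol*

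**What the plan says.** **Skip and restart (Protocol 5.1.3).** The section opens by saying that treatment will be skipped or discontinued for specified related events, then introduces its list with the softer statement that a skip may be necessary. The list includes any adverse event or any "laboratory abnormality or intercurrent illness that, in the judgment of the investigator, presents a substantial clinical risk to the subject with continued dosing", and any laboratory abnormality at or above the level of a "Grade 3 laboratory abnormality". Dosing restarts once the event falls to Grade 1 or less "severity or returns to baseline within 2 weeks of initial dose administration". Two restart cases follow: "If the adverse event has resolved, restart ipilimumab dosing at the next scheduled timepoint per protocol"; or, if the event has not resolved within the dosing window, "the next scheduled dose will be skipped and dosing will be resumed at the subsequently scheduled dose".

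**Permanent stop (Protocol 5.1.5.a).** Under "Permanently discontinue ipilimumab for any of the following", this section repeats the substantial-risk item with only two words changed (which for that, patient for subject). It also lists AST or ALT above 5 x ULN and bilirubin above 3 x ULN. No resolution or time condition is attached.

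**Liver rules elsewhere.** Section 5.1.10 withholds ipilimumab for Grade 2 hepatotoxicity and stops it permanently for Grade 3-5. Sections 5.1.11 and 6.4.1.e require abnormal liver tests to be managed by a hepatotoxicity algorithm held outside the protocol.

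**Leaving the study.** Section 5.1.4 requires both discontinuation of study therapy and withdrawal from the study when an adverse event, laboratory abnormality or intercurrent illness makes further treatment contrary to the patient's best interest. Section 3 (Follow-up) says that patients off ipilimumab for unacceptable toxicity are managed in follow-up with date of death recorded, and that those who discontinue ipilimumab are followed until death or study closure.

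**The concern.** One clinical judgment leads to two incompatible actions. A site that stops for good breaches neither section. A site that skips and restarts on resolution follows 5.1.3 and breaches 5.1.5.a. Patients with the same event could therefore be re-dosed at one site and stopped at another.

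First, this matters for safety conduct. It also matters for the feasibility objective in Protocol 2.2 (dose delays, reductions and exposure): the cycle and omission counts in SAP Table 13, and the listing of adverse events leading to discontinuation (Protocol 9.4.3), would partly reflect which section a site applied.

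The withdrawal wording in 5.1.4 is a separate problem and the only part that reaches the primary endpoint. Protocol 9.4.2.1 defines that endpoint as the actual proportion alive one year after the first ipilimumab dose. If withdrawal is taken to end follow-up, that status may never be collected for patients stopped for toxicity.

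**Working it through.** **1. Does any text settle the duplicated trigger?**
- The 5.1.3 lead-in names skipping, restarting and discontinuing together but does not say which trigger leads to which action.
- The exceptions in 5.1.5.b cover local anti-tumour inflammation, hospitalization for work-up, treated ocular toxicity and controlled endocrinopathy. None covers this trigger.
- 5.1.3 asks the investigator to contact the sponsor but gives no decision rule.
- Treating 5.1.5.a as controlling would leave the 5.1.3 item with no effect.

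The trigger is therefore unresolved within the protocol.

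**2. Doses at stake per patient.** Four doses are planned, one every 3 weeks (5.1.1). No make-up dose is assumed.

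| Trigger after dose | Total if stopped | Total if resolved before next dose | Difference | Total if one dose skipped | Difference |
|---|---|---|---|---|---|
| 1 | 1 | 4 | 4 - 1 = 3 | 3 | 3 - 1 = 2 |
| 2 | 2 | 4 | 4 - 2 = 2 | 3 | 3 - 2 = 1 |
| 3 | 3 | 4 | 4 - 3 = 1 | 3 | 3 - 3 = 0 |

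The range is 0 to 3 doses. The two-week limit in the restart sentence is not applied here: read literally it runs from the first dose, and it is unclear whether it governs both restart conditions.

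**3. Liver tests.** A Grade 3 or higher liver abnormality falls under the 5.1.3 laboratory item. The same result is a permanent stop under 5.1.10 (Grade 3-5) or, by its own cut-offs, under 5.1.5.a, and 5.1.11 sends it to the algorithm. Read together, these give one answer: stop. What is missing is any signal of this in 5.1.3. A patient without liver metastases whose AST exceeded 5 x ULN and then recovered to Grade 1 or less meets the 5.1.3 restart condition. That patient can also pass the 5.1.11 pre-dose limit of 2.5 x ULN, although 5.1.5.a bars re-dosing.

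**4. Primary endpoint.**
- The success rule is at least 17 of 56 evaluable patients alive at one year (Protocol 9.1). Evaluability needs one ipilimumab dose and full WBRT (9.2), so a skip-or-stop decision after dose 1 changes neither the rule nor the ipilimumab requirement for evaluability.
- The 5.1.4 wording is different. In SAP Table 19, a patient last known alive before one year falls in the no-follow-up row of the first crude rate and is excluded from the second.
- For scale, Protocol 1.3.4.a reports ipilimumab discontinued for adverse reactions in 10% of patients in the 3 mg/kg phase 3 study. Then 0.10 x 56 = 5.6, so about 5 to 6 patients could come under the conflicting instruction if that rate carried over to the WBRT combination.

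**The case against.** The strongest reply is that the conflict has little practical reach. The same investigator judges both the risk and the action, 5.1.3 calls for sponsor contact before any skip or stop, and most serious toxicities have their own explicit stop criteria. The substantial-risk item is a residual catch-all. That stands as a limit on size, but it does not tell a site which section to follow.

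On liver tests the reply mostly succeeds. A reader might infer that Grade 3 liver results are left without a governing rule. The documents do not support this: several specific, mandatory instructions agree against one general, permissive item. Early re-dosing is also unlikely in practice. Protocol Table 6 gives a median of 4.0 weeks to resolution for Grade 2-4 liver events (10 mg/kg data), and 5.1.10 requires corticosteroids tapered over a month for Grade 3-5. A missing carve-out remains, and it is worth closing because Protocol 1.3.4 reports fatal hepatic failure and mostly silent laboratory presentation.

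On 5.1.4, it can be said that Section 3 clearly intends follow-up after toxicity and that withdrawal need not end collection of vital status. Both are fair. But 5.1.4 is written as a requirement, and the two texts conflict as they stand.

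The treatment algorithms in the investigator brochure and SmPC were not available, so the absence of a ranking is established only for the protocol and SAP.

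**Conclusion.** The duplicated substantial-risk trigger is a definite inconsistency that should be corrected. Its size is 0 to 3 of 4 doses per affected patient; the number of such patients, and the number wrongly re-dosed, cannot be estimated from the documents. The liver issue is a missing carve-out in 5.1.3, not an absence of guidance.

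A reader might try to size the liver issue from Protocol Table 4, where severe-to-fatal hepatotoxicity is 1% and 2% in the two 3 mg/kg arms. Among 56 patients that gives 0.56 and 1.12 expected cases, and a chance of at least one of 1 - 0.99^56 = 0.430 and 1 - 0.98^56 = 0.677. These are chances of any such case, including fatal events and events after the last dose. They do not measure wrongful re-dosing.

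A reader might also infer that the skip-or-stop conflict threatens the trial's conclusion. It does not: it affects safety conduct and exposure summaries, and the 17-of-56 rule is untouched. Only the 5.1.4 contradiction can reach the primary endpoint, and only if withdrawal is taken to end survival follow-up. On the assumed 10% rate, 5 to 6 of 56 patients could come under it; how many would actually lose 1-year status is unknown.

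**What to change.** Three wording changes to the protocol:

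- **5.1.3 and 5.1.5.a:** limit the 5.1.3 item to risks expected to resolve, and the 5.1.5.a item to risks that persist or would recur on re-dosing. Simply deleting the 5.1.3 item is worse: permanent stop would become the only listed action for a transient risk below the other skip thresholds.
- **5.1.3:** add a sentence that the liver stop criteria in 5.1.5.a and 5.1.10 override the skip-and-restart rule. Keep it to the liver criteria. A blanket override would bring in the general severe-reaction stop in 5.1.5.a, which sits badly with the Grade 3 skin skip in 5.1.3 and the dermatitis withholding rule in 5.1.10.
- **5.1.4:** change the adverse-event item so that it stops study therapy only, with survival follow-up continuing as in Section 3.

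The cost is protocol text, with some care over how the revised criteria fit together. No visit, procedure or patient is added.
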